10.7. Appendix 7: ECG Findings of Potential Clinical Concern

ECG Findings That May Qualify as Adverse Events (AEs)

- Marked sinus bradycardia (rate <40 bpm) lasting minutes.
- New PR interval prolongation >280 msec.
- New prolongation of QTcF to >480 msec (absolute) or by ≥ 60 msec from baseline.
- New-onset atrial flutter or fibrillation, with controlled ventricular response rate: ie, rate <120 bpm.
- New-onset type I second-degree (Wenckebach) AV block of >30 seconds' duration.
- Frequent premature ventricular complexes (PVCs), triplets, or short intervals (<30 seconds) of consecutive ventricular complexes.

ECG Findings That May Qualify as Serious Adverse Events (SAEs)

- QTcF prolongation >500 msec.
- New ST-T changes suggestive of myocardial ischemia.
- New-onset left bundle branch block (QRS >120 msec).
- New-onset right bundle branch block (QRS >120 msec).
- Symptomatic bradycardia.
- Asystole:
 - In awake, symptom-free participants in sinus rhythm, with documented periods of asystole \geq 3.0 seconds or any escape rate <40 bpm, or with an escape rhythm that is below the AV node.
 - In awake, symptom-free participants with atrial fibrillation and bradycardia with 1 or more pauses of at least 5 seconds or longer.
 - Atrial flutter or fibrillation, with rapid ventricular response rate: rapid = rate >120 bpm.
- Sustained supraventricular tachycardia (rate >120 bpm) ("sustained" = short duration with relevant symptoms or lasting >1 minute).
- Ventricular rhythms >30 seconds' duration, including idioventricular rhythm (rate <40 bpm), accelerated idioventricular rhythm (40< x <100), and monomorphic/polymorphic ventricular tachycardia >100 bpm (such as torsades de pointes).
- Type II second-degree (Mobitz II) AV block.
- Complete (third-degree) heart block.

ECG Findings That Qualify as Serious Adverse Events

- Change in pattern suggestive of new myocardial infarction.
- Sustained ventricular tachyarrhythmias (>30 seconds' duration).
- Second- or third-degree AV block requiring pacemaker placement.
- Asystolic pauses requiring pacemaker placement.
- Atrial flutter or fibrillation with rapid ventricular response requiring cardioversion.
- Ventricular fibrillation/flutter.
- At the discretion of the investigator, any arrhythmia classified as an adverse experience.

The enumerated list of major events of potential clinical concern are recommended as "alerts" or notifications from the core ECG laboratory to the investigator and Pfizer study team, and not to be considered as all inclusive of what to be reported as AEs/SAEs.

Appendix 8: Abbreviations

The following is a list of abbreviations that may be used in the protocol.

Abbreviation	Term
Abs	absolute
AD	Atopic dermatitis
Ae	cumulative amount of drug recovered unchanged in urine
Ae%	cumulative amount of drug recovered unchanged in urine, expressed
	as percent of dose
AE	adverse event
ALT	alanine aminotransferase
aPTT	activated partial thromboplastin time
AST	aspartate aminotransferase
ATP	adenosine triphosphate
AUC	area under the curve
AUC ₂₄	area under the curve from zero to 24 hours
AUC _{inf}	area under the curve from zero to infinity
AUC _{last}	area under the plasma concentration-time curve from 0 to the time of last measurement
AUC _{tau}	area under the plasma concentration-time curve over the dosing interval
BA	bioavailability
BBS	Biospecimen Banking System
BCRP	breast cancer resistance protein
BID	twice daily
BMI	body mass index
BP	blood pressure
BUN	blood urea nitrogen
CFR	Code of Federal Regulations
CI	confidence interval
CIOMS	Council for International Organizations of Medical Sciences
СК	creatine kinase
CL	clearance
CLr	renal clearance
CL/F	clearance for extravascular dosing
C _{max}	maximum observed concentration
CO ₂	carbon dioxide (bicarbonate)
CRF	case report form
CRO	contract research organization
CRU	clinical research unit
CSR	clinical study report
СТ	clinical trial
CYP450	cytochrome P450

Abbreviation	Term
DCT	data collection tool
DDI	drug-drug interaction
DILI	drug-induced liver injury
DMC	data monitoring committee
DNA	deoxyribonucleic acid
EC	ethics committee
ECG	electrocardiogram
EDP	exposure during pregnancy
EMA	European Medicines Agency
EPO	erythropoietin
ET	early termination
EU	European Union
EudraCT	European Clinical Trials Database
FDA	Food and Drug Administration
FIH	first-in-human
FSH	follicle-stimulating hormone
GCP	Good Clinical Practice
GGT	gamma-glutamyl transferase
GM-CSF	granulocyte-macrophage colony-stimulating factor
HepBcAb	hepatitis B core antibody
HepBsAb	hepatitis B surface antibody
HepBsAg	hepatitis B surface antigen
HCG	serum pregnancy test
HCVAb	hepatitis C antibody
HIPAA	Health Insurance Portability and Accountability Act
HIV	human immunodeficiency virus
hr	hour
IB	Investigator's brochure
ICD	informed consent document
ICH	International Conference on Harmonisation
IC ₅₀	50% inhibitory concentration
IFN	interferon
IFN-α	interferon alpha
IFN-γ	interferon gamma
IL	interleukin
IND	Investigational New Drug
INR	international normalized ratio
IGA	Investigator's Global Assessment
IRB	institutional review board
IUD	intrauterine device
IV	intravenous
JAK	Janus kinase

Abbreviation	Term
K ₂ EDTA	dipotassium ethylenediaminetetraacetic acid
LFT	liver function test
log _e	logarithm
MATE	multidrug and toxin extrusion transporter
МСН	mean corpuscular hemoglobin
МСНС	mean corpuscular hemoglobin concentration
MCV	mean corpuscular volume
MDR	multi-drug resistance
mRNA	messenger ribonucleic acid
msec	millisecond
MTX	methotrexate
N/A	not applicable
NADPH	nicotinamide adenine dinucleotide phosphate
NASH	nonalcoholic steatohepatitis
NMN	N ¹ -methylnicotinamide
OAT	organic anion transporter
OATP	organic anion transporting polypeptide
OCT	organic cation transporter
PCD	primary completion date
PD	pharmacodynamic(s)
PEER	Pediatric Eczema Elective Registry
PGx	pharmacogenomic(s)
РК	pharmacokinetic(s)
POC	proof of concept
РТ	prothrombin time
РТТ	partial thromboplastin time
PVCs	premature ventricular complexes
QD	once daily
QTc	corrected QT interval
QTcF	QT interval calculated using Fridericia's correction factor
qual	qualitative
R _{ac}	accumulation ratio
RBC	red blood cell
RNA	ribonucleic acid
SAE	serious adverse event
SAP	statistical analysis plan
SCr	serum creatinine
SGOT	serum glutamic oxaloacetic transaminase
SGPT	serum glutamic pyruvic transaminase
SmPC	summary of product characteristics
SOC	system organ class
SOP	standard operating procedure

Abbreviation	Term	
SRSD	single reference safety document	
STAT	signal transducers and activators of transcription	
SUSARs	suspected unexpected serious adverse reactions	
$t_{\frac{1}{2}}$	apparent terminal half-life	
TB	Tuberculosis	
TBili	total bilirubin	
TEAEs	treatment emergent adverse events	
THC	tetrahydrocannabinol	
T _{max}	time to maximum concentration	
ТҮК	Tyrosine kinase	
UGT	uridine diphospho-glucuronosyltransferase	
ULN	upper limit of normal	
US	United States	
UVA	ultraviolet A light	
UVB	ultraviolet B light	
V/F	apparent volume of distribution	
Vc/F	apparent central volume of distribution	
Vp/F	apparent peripheral volume of distribution	
WBC	white blood cell	
WOCBP	women of childbearing potential	

1. AMENDMENTS FROM PREVIOUS VERSION(S)

None.

2. INTRODUCTION

PF-04965842 is a Janus kinase (JAK) 1 inhibitor that is currently being developed for the treatment of moderate to severe atopic dermatitis (AD).

Within vitro data indicating PF-04965842 may have the potential to inhibit multidrug and toxic compound extrusion transporter (MATE)1 and MATE2K, a clinical interaction study is needed to assess the effect of PF-04965842 on the activity of these transporters.

The primary purpose of this study is to assess the effect of PF-04965842 on the in vivo pharmacokinetics (PK) of metformin, a specific substrate for MATE1 and MATE2K.

2.1. Study Design

This is a Phase 1, randomized, 2-way crossover, open label study of the effect of PF-04965842 on metformin PK in healthy adult participants. The effect of PF-04965842 on N1-methylnicotinamide (NMN) PK and its correlation to the effect on metformin PK will also be assessed.

A total of approximately 12 healthy male and/or female participants will be enrolled in the study so that approximately 6 participants will be enrolled in each treatment sequence. Each treatment sequence will consist of 2 periods. Participants who discontinue from the study may be replaced at the sponsor's discretion. The replacement participant will receive the same treatment sequence as the participant who discontinued.

Participants will be screened within 28 days of the first dose of investigational product.

Participants will report to the clinical research unit (CRU) the day prior to Day 1 (ie, Day -1) dosing in Period 1 for both treatment sequences. In both sequences, participants will remain in the CRU for a total of 8 days and 7 nights (including Period 1 and Period 2). To adequately remove any drug effects of metformin (plasma half-life ~ 6 hours/whole blood half-life ~ 18 hours) from Period 1 to Period 2, there will be a minimum 4-day washout period between 2 dosing events. The minimum 3-day washout for PF-04965842 in Sequence 2 is sufficient as the half-life of PF-04965842 is ~3-5 hours. The metformin PK will be assessed over 48 hours. Participants will be assigned to one of the following 2 treatment sequences.

Table 1. Study Schematics

Sequence	Period 1	Washout Period	Period 2
1 (6 subjects)	Treatment A	At least 4 days from metformin administration	Treatment B
2 (6 subjects)	Treatment B	At least 4 days from metformin + PF-04965842 administration ^a	Treatment A

Abbreviation: *QD* = once daily.

a. At least a 3 day washout is required from the last dose of PF-04965842.

- *Treatment A (Reference): Single oral administration of metformin 500 mg on Day 1.*
- *Treatment B (Test): Concomitantly single oral administration of metformin 500 mg on Day 1 and oral administration of PF-04965842 200 mg QD for 2 days on Days 1-2.*

All treatments administered on Day 1 will be administered following a moderate-fat meal. PF-04965842 can be dosed with or without food on Day 2 in Treatment B.

2.2. Study Objectives

Primary Objective

- *To estimate the effect of PF-04965842 on MATE1/2K activity via the pharmacokinetic assessment of a single, oral dose of metformin in healthy participants.*

Secondary Objective

- *To evaluate the PK, safety and tolerability of a single oral dose of metformin when co-administered with PF-04965842.*

Exploratory/Tertiary Objectives

- *To evaluate the effects of PF-04965842 on N^l-methylnicotinamide.*
- *To correlate the effects of PF-04965842 on N^l-methylnicotinamide versus metformin.*
- *To enable exploratory research through the collection of banked biospecimens, unless prohibited by local regulations or ethics committee decision.*

3. INTERIM ANALYSES, FINAL ANALYSES AND UNBLINDING

No formal interim analysis will be conducted for this study. However, as this is an sponsor-open study, the sponsor may conduct unblinded reviews of the data during the course of the study for the purpose of safety assessment, facilitating dose-escalation decisions, facilitating PK/PD modeling, and/or supporting clinical development.

Final analysis will follow the official database release. As this will be an open-label study, there is no formal unblinding of the randomization code.

4. HYPOTHESES AND DECISION RULES

4.1. Statistical Hypotheses

There are no statistical hypotheses.

4.2. Statistical Decision Rules

There are no statistical decision rules.

5. ANALYSIS SETS

5.1. Pharmacokinetic (PK) Analysis Set

5.1.1. Concentration Analysis Set

The pharmacokinetic (PK) concentration population is defined as all enrolled subjects who received at least 1 dose of metformin and in whom at least 1 plasma concentration value is reported.

5.1.2. Parameter Analysis Set

The PK parameter analysis population is defined as all participants randomized and treated who have at least 1 of the PK parameters of primary interest in at least 1 treatment period.

5.2. Pharmacodynamic Analysis Set

None.

5.3. Safety Analysis Set

All participants randomly assigned to investigational product and who take at least 1 dose of investigational product. Participants will be analyzed according to the product they actually received.

5.4. Other Analysis Sets

None.

5.5. Treatment Misallocations

All analyses will be performed on an “as-treated” basis and will not include data from subjects who are randomized but not treated.

If a subject takes a treatment that is not consistent with the treatment they are randomized to, for example takes a treatment out of sequence or takes the same treatment twice, then they will be reported under the treatment that they actually receive for all safety, PK and pharmacodynamic analyses, where applicable.

5.6. Protocol Deviations

Subjects who experience events that may affect their PK profile (eg, lack of compliance with dosing) may be excluded from the PK analysis. At the discretion of the pharmacokineticist a concentration value may also be excluded if the deviation in sampling time is of sufficient concern or if the concentration is anomalous for any other reason.

A full list of protocol deviations will be compiled and reviewed to identify major and minor deviations prior to database closure.

5.6.1. Deviations Assessed Prior to Randomization

At Screening, the investigator will assess subjects against the inclusion and exclusion criteria as set out in Sections 4.1 and 4.2 of the protocol.

5.6.2. Deviations Assessed Post-Randomization

A full list of protocol deviations for the study report will be compiled prior to database closure. Any significant deviation from the protocol will be reviewed prior to database closure and a decision taken regarding evaluation for each analysis population.

6. ENDPOINTS AND COVARIATES

6.1. Efficacy Endpoint(s)

None.

6.2. Safety Endpoints

Any events occurring following start of treatment or increasing in severity will be counted as treatment emergent.

Events that occur in a non-treatment period (for example, Washout or Follow-up) will be counted as treatment emergent and attributed to the previous treatment taken.

The following data are considered in standard safety summaries (see protocol for collection days and list of parameters):

- *Adverse events;*
- *Laboratory data;*
- *Vital signs data;*
- *ECG results.*

6.2.1. Adverse Events

Any events occurring following start of treatment or increasing in severity will be counted as treatment emergent.

Events that occur in a non-treatment period (for example, Washout or Follow-up) will be counted as treatment emergent and attributed to the previous treatment taken.

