1.3. Schedule of Activities (SoA)

The SoA table provides an overview of the protocol visits and procedures. Refer to the STUDY ASSESSMENTS AND PROCEDURES section (Section 8) of the protocol for detailed information on each procedure and assessment required for compliance with the protocol.

The investigator may schedule visits (unplanned visits) in addition to those listed in the SoA table, in order to conduct evaluations or assessments required to protect the well-being of the participant.

Table 1.Schedule of Activities

Visit Identifier	Screening			Period 1			Period 2 ^a			ЕТ	Phone call
Days Relative to Day 1	-28 to -2	-1	1	2	3	4	1	2	3		28-35 days after last dose of metformin ^b
Informed Consent	Х										
Inclusion/Exclusion Criteria	Х	Х									
Medical, Drug, Tobacco and Alcohol History	Х										
Complete Physical Examination ^c		Х									
Demography, Height and Weigh	Х										
Serum FSH (Postmenopausal Females Only)	Х										
Serum Pregnancy Test (HCG) for WOCBP only	Х	Х							Х	Х	
Blood sampling for Pfizer Prep D1 banked sample(s) ^d			Х								
Urine Drug Screen	Х	Х									
Single 12-Lead ECG	Х		X ^e				X ^e		Х	Х	
Clinical Safety Labs (Blood and Urine)	Х	Х				Xf			Х	Х	
Contraception check	Х	Х							Х	Х	Х
Serology: HIV, HepBsAg, HepBcAb, HepBsAb, HCVAb testing	Х										
QuantiFERON [®] - TB Gold Test	Х										
Vital Signs and Oral Temperature	Х		X ^g				X ^g		Х	Х	
Moderate Fat Meal consumed prior to dosing			Х				Х				
Metformin Dosing ^h			Х				Х				
PF-04965842 Dosing (Sequence 1)							Х	Х			
PF-04965842 Dosing (Sequence 2)			Х	Х							
Metformin PK Blood Sampling			X ⁱ	\rightarrow	X ⁱ		X ⁱ	\rightarrow	X ⁱ		
Metformin PK Urine Sampling			X ⁱ	\rightarrow	X ⁱ		X ⁱ	\rightarrow	X ⁱ		
NMN PK Blood Sampling			X ⁱ	X ⁱ			X ⁱ	X ⁱ			

Table 1.Schedule of Activities

Visit Identifier	Screening	Period 1		Period 2 ^a			ET	Phone call			
Days Relative to Day 1	-28 to -2	-1	1	2	3	4	1	2	3		28-35 days after last dose of metformin ^b
NMN PK Urine Sampling			X ⁱ	X ⁱ			X ⁱ	X ⁱ			
CRU Confinement		Х	\rightarrow	\rightarrow	\rightarrow	\rightarrow	\rightarrow	\rightarrow	Х		
Serious and non-serious Adverse Event Monitoring	Х	\rightarrow	\rightarrow	\rightarrow	\rightarrow	\rightarrow	\rightarrow	\rightarrow	\rightarrow	\rightarrow	Х
Prior/Concomitant Treatment Assessment	Х	\rightarrow	\rightarrow	\rightarrow	\rightarrow	\rightarrow	\rightarrow	\rightarrow	\rightarrow	\rightarrow	Х

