Abbreviations: \rightarrow = ongoing/continuous event; CRU = clinical research unit; ECG = electrocardiogram; ET = early termination; FSH = follicle-stimulating hormone; HepBcAb = hepatitis B core antibody; HepBsAb = hepatitis B surface antibody; HepBsAg = hepatitis B surface antigen; HCVAb = hepatitis C antibody; HCG = Human Chorionic Gonadotropin; HIV = human immunodeficiency virus; hr = hour; NMN = N¹-methylnicotinamide; PK = pharmacokinetic; TB = tuberculosis; WOCBP = women of childbearing potential.

a. Day 1 of Period 2 will be at least 4 days after Day 1 of Period 1.

b. Phone contact to capture any potential AEs and concomitant treatment(s) and to confirm appropriate contraception usage.

c. After the complete physical examination on Day -1, further examinations will be performed at the discretion of the investigator.

d. If not collected on the designated collection day, collect at the next available time point when biospecimens are being collected in conjunction with a participant visit.

e. Perform single 12 lead ECG at pre-dose (before meal) and 2 hours post-dose.

f. Clinical safety labs will be collected before Period 2 Day 1.

g. Supine blood pressure, pulse rate and oral temperature pre dose and 2 hr post dose.

h. Participants will be dosed with metformin following a moderate-fat breakfast at approximately 08:00 AM (±2 hrs). On the day of co administration of metformin and PF-04965842, metformin will be administered with PF-04965842 concomitantly in no specific order, over no more than 5 minutes apart.

i. See pharmacokinetic sampling schema. (Table 2).

Table 2. Pharmacokinetic Sampling Schema

	Periods 1 and 2											
Visit Identifier	Day 1							Da	Day 2			
Hours After Dose on Day 1	0 ^a	0.5	1	2	4	6	8	12	16	24	36	48
Blood samples for												
PK blood sampling for metformin	X ^a	Х	Х	Х	Х	Х	Х	Х	Х	Х	Х	Х
PK blood sampling for NMN	X ^a	Х	Х	Х	Х	Х	Х	Х	Х	Х		
Urine samples for												
Predose PK spot urine blank	X ^a											
Start/Stop PK Urine collection for metformin concentrations ^{b,c}	Х←							\rightarrow X \leftarrow		→Х←	$\rightarrow X \leftarrow$	→Х
Start/Stop PK Urine collection for NMN ^{b,d}	Х←							→Х←		→Х		

Abbreviations: NMN = N1-methylnicotinamide; PK = pharmacokinetic.

a. Predose (metformin administration) sample collection.

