(Bell's palsy) and later developed herpes zoster (shingles). The incidence of normal and abnormal electrocardiogram (ECG) recordings were similar across all treatment groups at each time point. None of the abnormal ECG recordings were determined to be clinically significant by the investigator.

In the completed 12-week Phase 2b study (B7451006) in participants with AD, AEs and serious AEs (SAEs) were numerically higher in participants receiving PF-04965842 (10, 30, 100, and 200 mg QD) compared to placebo, but did not appear to increase with dose. The most common AEs were in the infections and infestations, skin and subcutaneous tissue disorders and gastrointestinal disorders system organ class (SOC), and the majority of the AEs were mild. The most commonly reported TEAE across all the treatment groups were dermatitis atopic (38 events), and viral upper respiratory tract infection (33 events). The most frequently reported treatment-related TEAE was nausea. There were 2 cases of non-serious herpes zoster, one in the 10 mg group (not treatment-related), and one in the 30 mg group (treatment-related). There were 2 participants (doses of ≥ 100 mg OD) with treatment related SAEs reported, the SAEs were Eczema herpeticum and Pneumonia. One participant randomized to the PF-04965842 10 mg group reported an SAE of malignant melanoma. Dose-dependent mean platelet count decreases from baseline were observed with a nadir at Week 4. At Week 4 the mean platelet count and the 90% confidence interval (CI) were within the normal reference range for both the 100 mg dose and 200 mg dose. In these treatment groups, the mean platelet count increased towards baseline after Week 4. There were no clinically significant findings in vital signs or physical examinations. Most of the ECG results were normal. The incidence of normal and abnormal ECG recordings was similar between PF-04965842 and placebo groups at each time point.

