4. STUDY DESIGN

4.1. Overall Design

This is a Phase 1, randomized, 2-way crossover, open label study of the effect of PF-04965842 on metformin PK in healthy adult participants. The effect of PF-04965842 on N^1 -methylnicotinamide (NMN) PK and its correlation to the effect on metformin PK will also be assessed.

A total of approximately 12 healthy male and/or female participants will be enrolled in the study so that approximately 6 participants will be enrolled in each treatment sequence. Each treatment sequence will consist of 2 periods. Participants who discontinue from the study may be replaced at the sponsor's discretion. The replacement participant will receive the same treatment sequence as the participant who discontinued.

Participants will be screened within 28 days of the first dose of investigational product. Participants will report to the clinical research unit (CRU) the day prior to Day 1 (ie Day -1) dosing in Period 1 for both treatment sequences. In both sequences, participants will remain in the CRU for a total of 8 days and 7 nights (including Period 1 and Period 2). To adequately remove any drug effects of metformin (plasma half-life ~ 6 hours/whole blood half-life ~ 18 hours) from Period 1 to Period 2, there will be a minimum 4-day washout period between 2 dosing events. The minimum 3-day washout for PF-04965842 in Sequence 2 is sufficient as the half-life of PF-04965842 is ~3-5 hours. The metformin PK will be assessed over 48 hours. Participants will be assigned to one of the following 2 treatment sequences (Table 3):

Sequence Period 1		Washout	Period 2		
Sequence 1 ($N = 6$)	Treatment A	At least 4 days from metformin administration	Treatment B		
Sequence 2 (N = 6)	Treatment B	At least 4 days from metformin + PF-04965842 administration ^a	Treatment A		

Table 3.Treatment Sequences

Abbreiviation: N = number of enrolled participants; QD = once daily.

Treatment A (Reference): Single oral administration of metformin 500 mg on Day 1.

Treatment B (Test): Concomitantly single oral administration of metformin 500 mg on Day 1 and oral administration of PF-04965842 200 mg QD for 2 days on Days 1-2.

a. At least a 3 day washout is required from the last dose of PF-04965842.

• All treatments administered on Day 1 will be administered following a moderate-fat meal. PF-04965842 can be dosed with or without food on Day 2 in Treatment B.

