6.2.2. Laboratory Safety Tests

Safety laboratory tests will be performed as described in the protocol.

To determine if there are any clinically significant laboratory abnormalities, the haematological, clinical chemistry (serum) and urinalysis safety tests will be assessed against the criteria specified in the sponsor reporting standards. The assessment will take into account whether each subject's baseline test result is within or outside the laboratory reference range for the particular laboratory parameter.

Baseline is defined as the last predose measurement taken in each study period.

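### Does crediting Sequence 2 follow-up events to metformin alone, with a lab baseline drawn after PF-04965842, spoil the safety comparison?

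*SAP*

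**What the plan says.** **Adverse events.** SAP 6.2 and 6.2.1 count any event in washout or follow-up as treatment emergent; such events "will be counted as treatment emergent and attributed to the previous treatment taken". SAP 8.3.4 then reports adverse events by treatment.

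**Laboratory baseline.** SAP 6.2.2: "Baseline is defined as the last predose measurement taken in each study period". Table 1 of the protocol (section 1.3) places safety laboratory draws at Screening, Day -1, Period 1 Day 4, Period 2 Day 3 and early termination. Footnote f, attached to the Period 1 Day 4 draw, reads "Clinical safety labs will be collected before Period 2 Day 1".

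**Timing.** Footnote a to the same table: "Day 1 of Period 2 will be at least 4 days after Day 1 of Period 1". For Sequence 2, SAP 2.1 adds "At least a 3 day washout is required from the last dose of PF-04965842". Protocol 4.1 states that "participants will remain in the CRU for a total of 8 days and 7 nights". The closing phone call is 28 to 35 days after the last metformin dose.

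**Status of the safety data.** Safety and tolerability of co-administration is a secondary objective. Protocol 9.1 applies no formal inference to safety or PK data, and SAP 4.1 and 4.2 state that there are no hypotheses and no decision rules.

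**The concern.** Sequence 2 takes metformin plus PF-04965842 first and metformin alone second. PF-04965842 stops on Period 1 Day 2, and metformin alone follows three days later. Under the attribution rule, the whole month of follow-up in these six participants then counts towards the Reference column. Protocol 2.2.4.1 lists infection, viral reactivation and falls in blood counts among the potential risks of JAK inhibitors, and reports from an earlier study that "Dose-dependent mean platelet count decreases from baseline were observed with a nadir at Week 4". If such effects appeared late, some would be shown against metformin alone and the contrast between the columns would shrink.

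The laboratory rule raises a related worry. No draw sits in the Period 2 columns before dosing. The only candidate for the Period 2 baseline is the Period 1 Day 4 sample, which is also the only scheduled Period 1 post-dose result. In Sequence 2 it could carry a PF-04965842 effect. Recovery from that effect would then look like a change on metformin, and a value already outside the reference range would alter how SAP 6.2.2 judges later results. At stake is the reading of the by-treatment safety tables. The primary endpoint, metformin renal clearance, is not touched.

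**Working it through.** **1. Calendar.** Call Period 1 Day 1 study day 1 and start Period 2 at the four-day minimum, on day 5. In Sequence 2 the last PF-04965842 dose is on day 2.
- Metformin gap: 5 - 1 = 4 days.
- PF-04965842 washout: 5 - 2 = 3 days.
- Confinement: Day -1 plus days 1 to 7 = 8 days and 7 nights.

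All three match the documents. The phone call falls between day 5 + 28 = 33 and day 5 + 35 = 40.

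**2. Sequence 2 time credited to metformin alone.**
- After the last PF-04965842 dose: 28/(33 - 2) = 28/31 = 90.3%, up to 35/(40 - 2) = 35/38 = 92.1%.
- After the first dose: 28/32 = 87.5%, up to 35/39 = 89.7%.

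These are shares of time, not of events. The four days from the first PF-04965842 dose to Period 2 dosing stay with the combination.

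**3. Both sequences, 6 participants each.**
- Metformin alone: 6 × 4 + 6 × 28 = 192, up to 6 × 4 + 6 × 35 = 234 participant-days.
- Combination: 6 × 28 + 6 × 4 = 192, up to 234.
- All time after a first PF-04965842 dose: 6 × 28 + 6 × 32 = 360, up to 6 × 35 + 6 × 39 = 444.
- Share of that time credited to metformin alone: 168/360 = 46.7%, up to 210/444 = 47.3%.

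**4. How far this could dilute a PF-04965842 effect.** The documents give no onset times, so a range must be assumed. Suppose a PF-caused event is equally likely on each of the W days after the last PF-04965842 dose, with W at least 3. Sequence 1 credits all of these days to the combination. Sequence 2 credits W - 3 of them to metformin alone. The share shown under metformin alone is 6(W - 3)/(12W):

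| W (assumed) | Share under metformin alone |
|---|---|
| 3 days | 0% |
| 7 days | 24/84 = 28.6% |
| 14 days | 66/168 = 39.3% |
| 28 days | 150/336 = 44.6% |

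The near-even split in the last row needs a flat risk over four weeks after two doses.

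**5. Drug remaining**, as 2^(-t/h) with h = 3 to 5 hours.
- At the Day 4 sample (about 48 hours after the last dose): 9.6 to 16 half-lives, at most 0.13% left.
- At Period 2 dosing (72 hours): 14.4 to 24 half-lives, under 0.005% left.

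**6. Would Day -1 be a better Period 2 baseline?** Let PF-04965842 shift a laboratory value by d at Day 4, let a fraction r of the shift recover by Period 2 Day 3, and let metformin do nothing.
- With the Day 4 baseline, metformin alone shows a false change of size r × d, in the direction of recovery.
- With Day -1, it shows a false change of size (1 - r) × d, in the direction of the PF-04965842 effect.

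Day -1 is better only if more than half the shift has recovered. For a persistent effect (r near 0), which is the case that prompts the worry, the Day 4 sample correctly shows no change on metformin alone and leaves the fall with the combination (Day 4 against Day -1). Day -1 would put that fall in the Reference column.

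**7. Would a table by exposure help?** Time on metformin alone before any PF-04965842 exists only in Sequence 1, Period 1: 6 × 4 = 24 participant-days. Set against 360 to 444 afterwards, that is 1:15 to 1:18.5. Raw counts would be higher after PF-04965842 even if it had no effect.

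**The case for a change.** The best case for acting is that a short half-life shows the drug has gone, not that its effects have ended. The protocol itself collects adverse events for at least 28 days after the last dose (8.3.1) and repeats clinically significant laboratory abnormalities found within 28 days (8.2.4). Balanced time does not cure dilution either: with similar amounts of post-PF follow-up in both columns, a late event is almost as likely to land in one as in the other. And read literally, SAP 6.2.2 leaves all 12 participants without a Period 2 laboratory baseline.

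Part of this stands. In Sequence 2, the metformin-alone column does not mean never exposed to PF-04965842, and a late event there should be read with its sequence and period in view. The SAP could also have named the Day 4 sample.

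The rest is weaker. The risk list in Protocol 2.2.4.1 gives no onset times. The Week 4 platelet nadir comes from a 12-week dosing study, in which the Week 4 means at 100 mg and 200 mg stayed within the normal range; it says little about two doses. The common events in healthy participants (diarrhea, nausea, vomiting, headache, dizziness) are plausibly acute, and any that arise before Period 2 dosing stay with the combination. A sample before Period 2 dosing does exist, as footnote f makes plain; only its column label sits in Period 1. SAP 8.3.5 does not specify a laboratory change-from-baseline summary, whereas 8.3.6 and 8.3.7 do so for vital signs and ECG.

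**Conclusion.** No change to the plan follows. Attribution to the last treatment taken is the usual crossover convention. Because follow-up comes after both drugs in both sequences, no tabulation rule can separate their late effects. About 90% of Sequence 2 time after PF-04965842 is credited to metformin alone, but serious dilution also needs PF-04965842 events spread over weeks after two doses, and the documents do not show that. With 12 participants, a descriptive summary and an investigator's causality assessment for each event (Protocol 10.3.3), a late event can be read individually.

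The baseline wording is a small gap with one sensible filling: the Period 1 Day 4 sample serves both as the Period 1 post-dose result and as the Period 2 baseline. Replacing it with Day -1 would be a trade-off that does worse for persistent effects, and a table by exposure would rest on 24 participant-days of comparison time.

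This rests on three assumptions: Period 2 starts at the four-day minimum, as the confinement length implies; all 12 participants complete; and the stated 3 to 5 hour half-life applies. Evidence of late effects after such a short exposure would strengthen the case for also showing events by sequence and period, but would not alter the renal clearance conclusion.
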